mRNA	messenger ribonucleic acid
NCS	not clinically significant
PP	Per-Protocol
PT	preferred term
SAE	serious adverse event
SAS	Statistical Analysis System
SD	Standard deviation
SOC	system organ class
TEAE	treatment-emergent adverse event
TLFs	Tables, listings, and figures
ULOQ	upper limit of quantification
WHODrug	World Health Organization Drug

1. Administrative Structure

This study is being conducted under the sponsorship of Moderna Therapeutics, Inc. The safety and immunogenicity statistical analyses are being performed under contract with PPD in collaboration with Moderna Therapeutics, Inc.

This statistical analysis plan has been written according to protocol VAL-181388-P101, Version 4.0, dated 30 August 2018.

2. Introduction

Chikungunya virus (CHIKV) is a mosquito-borne alphavirus posing a significant public health problem in tropical and subtropical regions. While chikungunya has been present in Africa for centuries, it has recently caused outbreaks and epidemics in new regions reflecting the increasing distribution of the *Aedes* mosquito. A chikungunya epidemic beginning in 2004 in Kenya, which spread to the Indian Ocean islands and to India, and was exported to nearly all regions of the world via infected travelers, resulted in millions of infected individuals and brought chikungunya to the attention of the western world. As of April 2016, chikungunya cases had been reported in 103 countries and territories around the world, including 46 countries and territories throughout the Americas ([Centers for Disease Control and Prevention 2016](#)). There are an estimated 3 million cases of chikungunya globally.

There are currently no effective therapies or approved vaccines to treat or prevent chikungunya, and effective mosquito control has proven challenging, even in higher income countries. Mosquito nets have limited effectiveness against the daytime-biting *Aedes* mosquito. Therefore, there is a need for a safe and effective prophylactic vaccine.

Of the new approaches currently in development, virus-like particle vaccines and live-attenuated vaccines show the greatest potential from preclinical data ([Wang et al 2008](#); [Akahata et al 2010](#); [Darwin et al 2011](#); [Brandler et al 2013](#)). However, there are significant potential drawbacks with these 2 vaccine approaches. The virus-like particle-based vaccines are typically challenging to manufacture, particularly within the context of a disease of greatest relevance to developing countries where it is desirable to keep the technology simple and cost of goods low. The live-attenuated vaccines, on the other hand, carry the well-known safety concerns normally associated with this type of technology (potential of break-through infections and possible central nervous system sequelae,

depending on the chosen virus backbone). Based on encouraging preclinical data with VAL-181388 and other similar messenger RNA (mRNA)-based vaccine candidates in the development pipeline, the Sponsor believes that VAL-181388 has the potential to be a tolerable and effective prophylactic vaccine against CHIKV.

3. Objectives

3.1. Primary Objective

The primary objective of this study is to assess the safety of VAL-181388 relative to placebo.

3.2. Secondary Objectives

The secondary objective of this study is to determine the immunogenicity of 3 dose levels of VAL-181388 to inform the choice of dose for further development of this vaccine. Immunogenicity assessment will be based on changes from baseline in the following:

- Serum neutralizing antibody titers to CHIKV
- Serum binding antibody titers to CHIKV-specific proteins

3.3. Exploratory Objectives

The exploratory objectives of this study are to:

- Assess the cross-reactivity of serum antibodies to related viruses, including alphaviruses and flaviviruses
- Explore other assays to characterize the immune response to CHIKV

4. Investigational Plan

4.1. Overall Study Design and Plan

This is a Phase 1, first-in-human, randomized, observer-blinded, placebo-controlled, dose escalation study to evaluate the safety and immunogenicity of 3 dose levels of VAL-181388 in healthy adult subjects (18 to 49 years of age, inclusive). VAL-181388 is an mRNA-based vaccine being developed for prevention of disease associated with CHIKV infection.

This is a 2-part study, with Part A including dose escalation and safety and immune testing through 28 days following the final vaccination. Once subjects complete Part A they will transition to Part B. Part B is a continued safety follow-up through 12 months and an assessment of immunogenicity and immune persistence at approximately 6 and 12 months after final vaccination.

Part A

In Part A, sequential dose escalation of VAL-181388 is planned in 3 dose level cohorts (25, 50, and 100 µg) with each subject receiving 2 vaccinations separated by 28 days. Subjects will be randomly assigned to receive either VAL-181388 or placebo.

For each cohort, a sentinel safety group of 4 subjects will be enrolled who will be randomly assigned to VAL-181388 or placebo (3:1) and followed for 7 days after the first vaccination with review of reactogenicity and safety laboratory results prior to randomizing the remainder of the cohort.

Dose Level Cohort Assignments: VAL-181388 (or placebo) administered intramuscular (IM) at Visit 1 and a second dose administered 28 days later (Visit 4).

Cohort 1 (N = 20): 25 µg VAL-181388 or placebo (ratio = 3:1)

Cohort 2 (N = 20): 50 µg VAL-181388 or placebo (ratio = 3:1)

Cohort 3 (N = 20): 100 µg VAL-181388 or placebo (ratio = 3:1)

VAL-181388 (or placebo) will be administered as an IM injection (0.5 mL) into the deltoid muscle, preferably in the non-dominant arm, as a 2-dose schedule; the first dose will be given at Visit 1 followed by a second dose 28 days later. VAL-181388 accountability, dose preparation, and administration will be performed by unblinded pharmacy personnel or unblinded designees who will not participate in any other aspect of the study. The remainder of the site staff and all subjects will remain blinded to treatment assignment.

Subjects will be instructed on recording solicited (local and systemic reactogenicity events) and unsolicited adverse events (AEs), temperature, and medications (prescription or over-the-counter) on their memory aid (ie, diary card). Subjects will also be asked to call/return to the clinic within 24 hours if reactogenicity reaches Grade 3 or higher during the first 7 days following vaccination. As standard practice, a reminder call will be made to

the subject by the site at least once during the first 7 days following each vaccination to answer any questions and ensure that the memory aid is being completed correctly and consistently.

Safety assessments will include toxicity grading of solicited (local and systemic reactogenicity events) and unsolicited AEs, vital sign measurements, physical examination findings, and clinical laboratory test results for hematology, serum chemistry, coagulation, and urinalysis. All unsolicited AEs will be collected and additional specific categories will include serious AEs (SAEs); AEs of special interest (AESIs); and medically attended AEs. Subjects will self-report (using a memory aid) solicited (local and systemic reactogenicity events) and unsolicited AEs and medication usage (over-the-counter and prescription) through 28 days after each vaccination. In addition, subjects will be instructed to measure their oral temperature daily for the first 7 days post vaccination and record that measure on the memory aid. At applicable clinic visits, the investigator will review the entries on the memory aid with the subject to ensure consistency.

Part A is concluded for each subject when they return to the clinic for Visit 7 (28 days after final vaccination). At that time, subjects will transition to Part B of the study.

Part B

To monitor for longer-term safety and immune persistence, each subject will be entered into a continued blinded follow-up period (Part B). This period will be conducted such that subjects and safety monitors will remain blinded to treatment assignment. Part B of the study is initiated for a subject once they have returned for Visit 7 (28 days after the second vaccination).

Once entered into Part B, each safety contact will occur by telemedicine (eg, telephone, text message, internet) every 28 (± 7) days, and blood samples for immune persistence will be collected from each subject on Visit 12 (168 [± 15] days after the second vaccination) and Visit 19 (364 [$+15$] days after the second vaccination) of the study. Each safety contact will capture outcomes of any AESI or SAE that remains unresolved since the last visit or is newly identified through scripted query.

The telemedicine visits may require additional data through medically attended visits, in addition to medications and vaccinations taken by the subject during this time. Subjects will have consented during study enrollment to allow access to additional medical records

needed to complete Part B, thereby allowing the blinding of the treatment assignment to be maintained.

4.2. Study Endpoints

The following are the safety (primary) endpoints:

Part A:

- Solicited AEs (local and systemic reactogenicity events) collected for 7 days following each vaccination with toxicity grading
- Unsolicited AEs collected for 28 days following each vaccination; additional classification if serious, medically attended, or an AESI
- Safety laboratory test results (serum chemistry, hematology, coagulation, and urinalysis) with toxicity grading
- Vital sign measurements with toxicity grading and physical examination findings

Part B:

- Serious AEs and AESIs through 1 year (or until resolved, whichever occurs first) following the last vaccination

The immunogenicity assessments are as follows:

Part A:

- Serum neutralizing antibody titers to CHIKV proteins (baseline and 28 days after each vaccination)
- Serum binding antibody titers (immunoglobulin G [IgG]) to CHIKV proteins (baseline and 28 days after each vaccination)
- Exploratory antibody assays may be performed with excess serum to assess for cross-reactivity to related viruses at the discretion of the Sponsor

- Additional exploratory assays based upon current research may be performed with excess serum to better characterize the immune response to the CHIKV proteins at the discretion of the Sponsor

Part B:

- Serum neutralizing antibody titers to CHIKV (at 6 and 12 months after the last vaccination)
- Serum binding antibody titers (IgG) to CHIKV-specific proteins (at 6 and 12 months after the last vaccination)
- Exploratory antibody assays may be performed with excess serum to assess for cross-reactivity to related viruses at the discretion of the Sponsor
- Additional exploratory assays based upon current research may be performed with excess serum to better characterize the immune response to the CHIKV proteins at the discretion of the Sponsor

5. General Statistical Considerations

All data collected will be presented in listings. Subjects will be identified in the listings by the subject identification number concatenated with the site number.

Data from subjects excluded from an analysis set will be presented in the data listings but not included in the calculation of summary statistics for the corresponding analysis set.

Data from subjects receiving placebo will be pooled across cohorts for all presentations.

Unless otherwise specified, the following treatment groups will be used for summary purposes:

- 25 µg VAL-181388
- 50 µg VAL-181388
- 100 µg VAL-181388
- Placebo

For categorical variables, frequencies and percentages will be presented. Continuous variables will be summarized using descriptive statistics (number of subjects, mean, median, standard deviation [SD], minimum, and maximum).

For the summary statistics of all numerical variables unless otherwise specified, minimum and maximum will be displayed to the same level of precision as reported. Mean, median, and confidence intervals (CIs) will be displayed to one level of precision greater than the data collected. Standard deviation will be displayed to two levels of precision greater than the data collected. P-values will be rounded to three decimal places.

When count data are presented, the percentage will be suppressed when the count is zero in order to draw attention to the non-zero counts. A row denoted “Missing” will be included in count tabulations where specified on the shells to account for dropouts and missing values. The denominator for all percentages will be the number of subjects in that treatment within the analysis set of interest, unless otherwise specified.

For the change from Baseline safety summaries, Baseline will be defined as the last non-missing measurement (including repeated and unscheduled assessments) before the first vaccination.

For the immunogenicity analyses, Baseline will be defined as the assessment before the first vaccination.

Study day will be calculated relative to the most recent vaccination. Study day prior to the first vaccination will be calculated as: date of assessment/event – date of first vaccination; study day on or after the date of first vaccination but before the second vaccination (if applicable) will be calculated as: date of assessment/event – date of first vaccination + 1; study day on or after the date of second vaccination will be calculated as: date of assessment/event – date of second vaccination + 1.

Antibody values reported as below the lower limit of quantification (LLOQ) will be replaced by $0.5 \times \text{LLOQ}$. Values that are greater than the upper limit of quantification (ULOQ) will be converted to the ULOQ. Missing results will not be imputed.

All analyses will be conducted using Statistical Analysis System (SAS) Version 9.3 or higher.

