Subjects will be instructed on recording solicited (local and systemic reactogenicity events) and unsolicited AEs, temperature, and medications (prescription or over-the-counter) on their memory aid (ie, diary card). Subjects will also be asked to call/return to the clinic within 24 hours if reactogenicity reaches Grade 3 or higher during the first 7 days following vaccination. As standard practice, a reminder call will be made to the subject by the site at least once during the first 7 days following each vaccination to answer any questions and ensure that the memory aid is being completed correctly and consistently.

Safety assessments will include toxicity grading of solicited (local and systemic reactogenicity events) and unsolicited AEs, vital sign measurements, physical examination findings, and clinical laboratory test results for hematology, serum chemistry, coagulation, and urinalysis. All unsolicited AEs will be collected and additional specific categories will include SAEs; AEs of special interest (AESIs); and medically attended AEs. Subjects will self-report (using a memory aid) solicited (local and systemic reactogenicity events) and unsolicited AEs and medication usage (over-the-counter and prescription) through 28 days after each vaccination. In addition, subjects will be instructed to measure their oral temperature daily for the first 7 days post vaccination and record that measure on the memory aid. At applicable clinic visits, the investigator will review the entries on the memory aid with the subject to ensure consistency.

Safety laboratory tests will be performed at Screening, on vaccination days (before dosing), and at 7 (+3) days after each vaccination. At 17 ( $\pm 3$ ) days following each vaccination and at 28 (+7) days after the second vaccination, safety laboratory tests will be performed for coagulation and liver function tests only. The sentinel safety group will also have coagulation

and liver function tests collected at 21 (+3) days after the first vaccination. Additional safety laboratory tests may be conducted at any time by the investigator if deemed necessary.

Blood samples for immunogenicity will be collected on dosing days (pre-dose) and at 28 (+7) days after the final vaccination.

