### **3.6.5.2      Safety Analyses**

Data for subjects receiving placebo will be pooled across all dose levels for all presentations. Reactogenicity will be summarized by dose levels (25, 50, or 100 µg or placebo), vaccination (first or second), duration, relationship to study vaccine, and severity. Adverse events will be coded by preferred term and system organ class using MedDRA and summarized by part, treatment, vaccination (first or second), and overall. Adverse events will also be summarized by severity and relationship to study vaccine. Descriptive statistics will be presented and the difference in the proportion of AEs will be provided comparing each dose level with placebo recipients pooled across all dose levels. Adverse events for subjects in the safety cohort for each dose level will be provided in a separate subject listing. Adverse events leading to withdrawal, AESIs, medically attended AEs, and SAEs will be provided by subject in a listing.

Safety data from clinical laboratory test results and vital sign measurements will be graded by severity and analyzed by treatment group and vaccination (first or second). Absolute and change from baseline values will be provided according to the toxicity table, along with mean, median, and standard deviation. Results of hematology, serum chemistry, coagulation, and urinalysis assessments; urine drug screen; and pregnancy testing will be listed for all subjects randomly assigned to receive study treatment.

Medical history data for all subjects randomly assigned to receive study treatment will be presented by subject in a listing.

Baseline demographic and background variables will be summarized by treatment group and cohort for all subjects. The number of subjects who enroll in the study and the number and percentage of subjects who complete the study will be presented. Frequency and percentage of subjects who withdraw or discontinue from the study, and the reason for withdrawal or discontinuation, will also be summarized.

Prior and concomitant medication will be listed (with start and stop dates) for each subject and summarized by common medical dictionary coding. Any vaccinations that occur during the trial conduct will also be captured and summarized.

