- b. Full physical examination at Screening; symptom-directed (targeted) physical examination at all other scheduled time points. Interim physical examinations will be performed at the discretion of the investigator, if necessary. Height and weight will be measured and body mass index calculated at Screening only.
- c. Assessment to be performed before study drug administration.
- d. Vital sign measurements (systolic and diastolic blood pressures, heart rate, respiratory rate, and body temperature) on Visits 1 and 4 will be collected once before study drug administration and at least 1 hour after study drug administration (before subjects are discharged). Vaccination cannot occur if systolic or diastolic blood pressure, heart rate, or respiratory rate measurements show Grade 2 or higher toxicity after 2 measurements; if a subject has an acute illness; or if a subject has an oral temperature >38°C.
- e. Assessment to be performed before and after study drug administration.
- f. Serology testing will include hepatitis B surface antigen, hepatitis C virus antibody, and human immunodeficiency virus type 1 and 2 antibodies.
- g. Hematology, serum chemistry, coagulation, and urinalysis assessments.
- h. Safety laboratory tests for albumin, bilirubin (total and direct), prothrombin time, partial thromboplastin time, alkaline phosphatase, alanine aminotransferase, aspartate aminotransferase.
- i. The drug screen will include alcohol, opiates, cocaine, phencyclidine, amphetamines, benzodiazepines, and methadone.
- j. To confirm post-menopausal status, as needed.
- k. Excess serum from immunogenicity may be used for future research at the discretion of the Sponsor to better characterize the immune response to the CHIKV protein.
- l. Subjects will be instructed on how to complete the memory aid prior to discharge from the clinic at Visit 1. Subjects will be instructed to call or return to the clinic within 24 hours if reactogenicity reaches Grade 3 or higher during the first 7 days following vaccination.

- m. Adverse events will be assessed from the time of study drug administration on Visit 1 through Visit 7. However, for the time period after the informed consent form is signed until before receiving the study drug, AEs will only be recorded when they are defined as one or more of the following: serious AEs, AEs of special interest, AEs leading to study withdrawal.

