clinically significant (NCS).” Investigators should use their clinical judgment when considering the clinical significance of any abnormal laboratory findings. All laboratory test values with a toxicity score of Grade 3 or greater will be entered as AEs. Any additional laboratory test value that is determined to be clinically significant will also be recorded as an AE, should that be considered the primary diagnosis. In such instances, the abnormal value and grade will be documented on the AE page of the eCRF. The investigator will continue to monitor the subject with additional assessments until the values have reached the reference range or the values at Screening or until the investigator determines that follow-up is no longer medically necessary. The only exception to this rule would be a laboratory test value that is associated with an identified ongoing AE where that event would be the classifying AE.

All laboratory test results will be presented in the data listings. The results that are outside the reference ranges will be flagged in the data listings. The abnormalities meeting the toxicity grading criteria (Grade 2 or higher) in any safety laboratory will be listed separately. If a subject has a laboratory test with Grade 2 or higher abnormality at any post vaccination visit, then all results for that subject and laboratory test will be presented in the listing.

For hematology, serum chemistry, coagulation, and numeric urinalysis test results, the observed values and changes from Baseline on Days 7, 17, 28 after each vaccination and for sentinel safety subjects also on Day 21 post first vaccination will be summarized by treatment groups as defined in Section 5. These laboratory tests will also be summarized by the toxicity grades.

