9.3. Vital Sign Measurements

Vital sign measurements will include systolic and diastolic blood pressures, heart rate, respiratory rate, and body temperature. Vital signs will be measured in Part A at Screening, before and after vaccination on the day of the first vaccination, on Days 1 and 2 (only for sentinel safety subjects), 7, 21 (only for sentinel subjects), and 28 (before second vaccination) post first vaccination, as well as after vaccination on the day of the second vaccination, and on Days 7 and 28 post second vaccination.

If any of the vital sign measurements meet the toxicity grading criteria for clinical abnormalities of Grade 2 or higher, the abnormal value and grade will be documented on

the AE page of the eCRF (unless there is another known cause of the abnormality and that would result in an AE classification).

The vital sign measurements will be presented in a data listing. The values meeting the toxicity grading criteria will be flagged in the data listing. Observed values and changes from Baseline will be summarized by treatment groups as defined in Section 5.

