- b. Full physical examination at Screening; symptom-directed (targeted) physical examination at all other scheduled time points. Interim physical examinations will be performed at the discretion of the investigator, if necessary. Height and weight will be measured and body mass index calculated at Screening only.
- c. Assessment to be performed before study drug administration.
- d. Vital sign measurements (systolic and diastolic blood pressures, heart rate, respiratory rate, and body temperature) on Visits 1 and 4 will be collected once before study drug administration and at least 1 hour after study drug administration (before subjects are discharged). Vaccination cannot occur if systolic or diastolic blood pressure, heart rate, or respiratory rate measurements show Grade 2 or higher toxicity after 2 measurements; if a subject has an acute illness; or if a subject has an oral temperature >38°C.
- e. Assessment to be performed before and after study drug administration.
- f. Serology testing will include hepatitis B surface antigen, hepatitis C virus antibody, and human immunodeficiency virus type 1 and 2 antibodies.
- g. Hematology, serum chemistry, coagulation, and urinalysis assessments.
- h. Safety laboratory tests for albumin, bilirubin (total and direct), prothrombin time, partial thromboplastin time, alkaline phosphatase, alanine aminotransferase, aspartate aminotransferase.
- i. The drug screen will include alcohol, opiates, cocaine, phencyclidine, amphetamines, benzodiazepines, and methadone.
- j. To confirm post-menopausal status, as needed.
- k. Excess serum from immunogenicity may be used for future research at the discretion of the Sponsor to better characterize the immune response to the CHIKV protein.
- l. Subjects will be instructed on how to complete the memory aid prior to discharge from the clinic at Visit 1. Subjects will be instructed to call or return to the clinic within 24 hours if reactogenicity reaches Grade 3 or higher during the first 7 days following vaccination.
- m. Adverse events will be assessed from the time of study drug administration on Visit 1 through Visit 7. However, for the time period after the informed consent form is signed until before receiving the study drug, AEs will only be recorded when they are defined as one or more of the following: serious AEs, AEs of special interest, AEs leading to study withdrawal.

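### Vital signs taken an hour after dose 2 are compared with a reading from before dose 1, although a same-day pre-dose reading is collected

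*SAP*

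**What the plan says.** SAP Section 5 (General Statistical Considerations) gives one rule for change-from-baseline safety summaries: "Baseline will be defined as the last non-missing measurement (including repeated and unscheduled assessments) before the first vaccination". The same section restarts the study-day count at the second vaccination, so the clock is reset at dose 2 but the baseline is not.

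The rule is applied after both doses. SAP 9.2 summarizes, for laboratory tests, "the observed values and changes from Baseline on Days 7, 17, 28 after each vaccination". SAP 9.3 lists vital sign times that include the pre-dose reading on Day 28 and continues "as well as after vaccination on the day of the second vaccination, and on Days 7 and 28 post second vaccination". It then says "Observed values and changes from Baseline will be summarized by treatment groups as defined in Section 5". Neither document names a baseline for the second vaccination.

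A complete pre-dose-2 set is scheduled. Footnote d of the Part A schedule of events (SAP Section 13) says that vital signs "on Visits 1 and 4 will be collected once before study drug administration and at least 1 hour after study drug administration". Protocol 3.1 says "Safety laboratory tests will be performed at Screening, on vaccination days (before dosing), and at 7 (+3) days after each vaccination", and footnote g of Protocol Table 6-1 gives the Visit 4 content as "Hematology, serum chemistry, coagulation, and urinalysis assessments".

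Protocol 3.6.5.2 says that laboratory and vital sign data "will be graded by severity and analyzed by treatment group and vaccination (first or second". It asks for change from baseline without saying which baseline belongs to which vaccination.

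**The concern.** A reading an hour after an injection is informative mainly against a reading shortly before it. For dose 1 the plan makes that comparison, because the last value before the first vaccination is normally the Visit 1 pre-dose reading. For dose 2 it does not: the reference is about a month old, and the same-day pre-dose value serves only as the Day 28 result after dose 1.

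Vital signs are among the primary safety endpoints (Protocol 3.6.1). Protocol 1.3 names an acute, hypersensitivity-like reaction related to complement activation as a possible risk. A reader of tables laid out by vaccination would naturally compare the acute change after dose 1 with that after dose 2. As planned, the two are different quantities: the first is a change across an injection, the second a change across an injection plus a month that includes the whole response to dose 1.

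**Working it through.** The plan states no SD, correlation or precision target for these variables, so there is no figure of its own to reproduce. The timing comes from the documents. The variability figures are assumptions, shown as a range.

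**1. Age of the reference value.** Dose 2 is given 28 to 35 days after dose 1 (Protocol 3.1). The post-dose-2 windows come from the Part A schedule. Days since dose 1 are the sums of the two ranges.

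| Assessment | Days since dose 1 (planned reference) | Days since dose 2 (Visit 4 pre-dose reference) |
|---|---|---|
| Visit 4, at least 1 hour after dosing | 28–35 | 0 |
| Visit 5 | 35–45 | 7–10 |
| Visit 6 (laboratory only) | 42–55 | 14–20 |
| Visit 7 | 56–70 | 28–35 |

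A pause suspends the vaccination window (Protocol 3.4.2.2), so the first column can be longer. At Visit 1 the 1-hour reading has a reference 0 days old.

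**2. What the planned change contains.** For any subject,

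(post-dose-2 − pre-dose-1) = (pre-dose-2 − pre-dose-1) + (post-dose-2 − pre-dose-2).

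The first term on the right is whatever was already there before the second injection. As an illustration in SD units (σ): if a shift of 0.25σ remains at Visit 4 and persists, an acute dose-2 effect of 0.50σ is tabulated as 0.25 + 0.50 = 0.75σ. If the leftover shift is −0.50σ, the same effect is tabulated as 0. Pooled placebo (3 × 5 = 15 subjects) is measured the same way, which removes time trends common to both groups but not a leftover vaccine effect.

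**3. Noise in the 1-hour change.** Let sb be the between-day and sw the within-visit SD for one subject.

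- Same-visit change: SD = √2 × sw, because the day's level cancels.
- Change across days: SD = √(2 × (sb² + sw²)).
- Ratio: √(1 + (sb/sw)²).

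Assumed systolic values, in mmHg:

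| sb | sw | Same-visit SD | Across-day SD | Ratio |
|---|---|---|---|---|
| 6 | 4 | √2 × 4 = 5.7 | √(2 × 52) = 10.2 | 1.8 |
| 8 | 5 | √2 × 5 = 7.1 | √(2 × 89) = 13.3 | 1.9 |
| 10 | 5 | √2 × 5 = 7.1 | √(2 × 125) = 15.8 | 2.2 |

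If sb were 0 the ratio would be 1, so the loss rests on between-day variation being non-trivial.

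**4. Laboratory values and later vital signs.** A Visit 5 value compared with the Visit 4 pre-dose value is also a comparison across days. The same formula, √(2 × (sb² + sw²)), applies with either baseline, and the ratio is 1.0. A loss would appear only if within-subject correlation were higher over the shorter interval. With SD = σ√(2(1 − ρ)), correlations of 0.6 (longer interval) and 0.8 (shorter) give a ratio of √(0.4/0.2) = 1.41. Correlations of 0.8 and 0.7 give √(0.2/0.3) = 0.82. The documents do not decide between these cases.

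**5. What does not depend on the choice.** The grades in Protocol Tables 6-3 and 6-4 use fixed limits, multiples of the upper limit of normal or clinical criteria, except the two hemoglobin change rows. The pause rules (Protocol 3.4.2.2) and the data reviewed for escalation (Protocol 3.4.2.1) use grades and adverse events, not mean change.

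**The case against.** The strongest defence is that the pre-dose-1 value is the only reference free of vaccine exposure and is the right one for cumulative toxicity. Placebo is measured the same way, which suits an objective stated relative to placebo. A pre-dose-2 baseline has a bias of its own: if a leftover 0.25σ fades by the later reading, a 0.50σ dose-2 effect shows as 0.25σ. All of this stands, and it is why the existing change should be kept. It bears little on the 1-hour reading, since an effect that has lasted 28 days is unlikely to fade within an hour.

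A second defence is that laboratory carry-over is visible. SAP 9.2 also tabulates Day 28 after dose 1, so an ALT rise of 20 U/L present at Visit 4 and unchanged at Visit 5 appears as +20 in both rows. This stands too. The mean change since dose 2 can be recovered by subtraction when the same subjects contribute. Its SD, median and range cannot be read from the tables, although all values are listed.

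Three stronger readings are tempting, and the documents do not support them.

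- A reader might infer that all post-dose-2 changes are less precise. Step 4 of the working shows no loss for laboratory values or later vital signs under the model that gives the loss for the 1-hour reading.
- A reader might infer that the SAP contradicts the protocol. Protocol 3.6.5.2 asks for analysis by vaccination but defines no baseline per dose.
- A reader might infer that an acute reaction could be missed. Protocol 1.3 describes clinical signs of complement activation as far less likely with intramuscular dosing. Such reactions are also sought through clinic observation for at least an hour, adverse event reporting and a pause rule that covers systemic hypersensitivity.

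Finally, confidence intervals are planned only for immunogenicity, so the noise would show in the tabulated SD and range rather than in an interval or a test.

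**Conclusion.** The point holds in a limited form. The vital sign change at least 1 hour after dose 2 is taken against a value 28 to 35 days old, or older, when a same-day value exists. It is therefore not comparable with the dose-1 change and includes any shift present before the second injection; both follow from the documents and the identity alone. It is also noisier, by a factor of about 1.8 to 2.2 for systolic pressure, if the assumed SDs (6 to 10 mmHg between days, 4 to 5 mmHg within a visit) are near the truth.

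For laboratory values and later vital signs the planned change is a valid cumulative measure. The gap there is only that it does not isolate change since dose 2. This is a cheap improvement to a descriptive summary, not an error that affects grading (hemoglobin change apart), pausing or escalation.

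**What to change.** - **SAP Sections 5 and 9.3:** define a second baseline, the last available value before the second vaccination (normally Visit 4 pre-dose), and use it for the same-day vital sign change after dose 2. Show that change beside the dose-1 same-day change.
- **SAP 9.2 and 9.3, as a supplement:** add a change-from-pre-dose-2 column for laboratory results and later vital signs after dose 2. Under the schedule, full laboratory panels contribute at Visit 5 only; Visits 6 and 7 have the liver and coagulation subset.
- **Keep the pre-dose-1 change** as the cumulative measure, label the two columns clearly, and state that the new baseline serves the change summaries only and leaves grading as it is.

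The cost is a few lines of SAP text and one table column; all values are already collected. The drawback is that the second baseline can carry a fading dose-1 effect, so neither column should be shown without the other.
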